3.9 Statistical Analysis Plan

The data analysis will be done using the SPSS version 26.0 Descriptive date will be expressed as mean \pm standard deviation (SD) for numerical data and frequency (percentage) for categorical data. Independent t-test will be used to analyse the primary objective. Secondary objective will be analyzed using logistic regression. A value of $P < 0.05$ is considered statistically significant. The data collected will be analyzed using an per protocol basis.

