Study Population	All adult patients with arteriovenous access flow dysfunction in Hospital Kuala Lumpur and University Malaya Medical Centre during the period 1 July 2023 – 30 June 2024.
Study Design	A randomized controlled study. Selected subjects will be randomized into ultrasound-guided fistuloplasty and fluoroscopy-guided fistuloplasty groups in a ratio of 1:1
General Objective	To investigate patencies in patients with arteriovenous access flow dysfunction receiving ultrasound-guided fistuloplasty versus fluoroscopy-guided fistuloplasty at 6 months
Specific Objectives	
 To investigate patencies in patients with arteriovenous access flow dysfunction receiving ultrasound-guided fistuloplasty versus fluoroscopy-guided fistuloplasty at 6 months, To capture data regarding variables that may affect patency of arteriovenous access flow dysfunction post ultrasound-guided fistuloplasty versus fluoroscopy-guided fistuloplasty, To compare technical success in patients with arteriovenous access flow dysfunction receiving ultrasound-guided fistuloplasty versus fluoroscopy-guided fistuloplasty, and To compare complication rates in patients with arteriovenous access flow dysfunction receiving ultrasound-guided fistuloplasty versus fluoroscopy-guided fistuloplasty.
Study endpoints/outcomes	(a) Patency of arteriovenous fistula over a period of six months post fistuloplasty; (b) Resolution of symptoms; (c) Technical success; (d) Percentage increase in volume flow.
Sample Size	54 subjects.
Study Duration	1 July 2023 - 31 December 2024.

1. Background and Significance

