3.1 Study Type and Design

This is an experimental study employing a prospective randomized controlled trial.

The primary outcome would be to compare the patency of arteriovenous fistula at one, three and six months.

Secondary outcomes shall include:

- To capture data regarding variables that may affect patency of arteriovenous access flow dysfunction post ultrasound-guided fistuloplasty versus fluoroscopy-guided fistuloplasty,
- To compare technical success (defined as clinical palpable thrill, radiographic finding of less than 30% recoil and ultrasonographic finding of continuous segment of dilated vein to 5-6mm and continuous flow rate of more than 500ml/min) in patients with arteriovenous access flow dysfunction receiving ultrasound-guided fistuloplasty versus fluoroscopy-guided fistuloplasty and
- To compare complication rates in patients with arteriovenous access flow dysfunction receiving ultrasound-guided fistuloplasty versus fluoroscopy-guided fistuloplasty

Patients are randomized using simple randomization method. Treatment plans are divided equally between ultrasound-guided fistuloplasty and fluoroscopy-guided fistuloplasty. An application “sealedenvelope.com” is used for this purpose. The application does this via a built in random number generator.

After assessing for eligibility, patients will be randomized equally with a ratio 1:1 to ultrasound-guided fistuloplasty group and fluoroscopy-guided fistuloplasty group.

Both interventions will be done in operation theatre to maintain sterility. After cleaning and draping the area of interest, local anaesthesia is given to the puncture site. A puncture needle is used to gain access to the arteriovenous fistula followed by a guide wire. Then, a sheath with an appropriate size is placed and a balloon catheter of adequate size is inserted over the guide wire and inflated for 2 minutes. Ultrasound is used in the subject group to monitor technical success. On table visualization of continuous segment of dilated vein to 5-6mm and continuous flow rate of more than 500ml/min signifies the end points of the procedure.

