Fluoroscopy is used in the control group to assess for technical success. On table fistulogram visualization of less than 30% recoil of the target lesion signifies technical success. After a satisfactory result, a figure of 8 suture is placed with manual inflow occlusion. Post procedure, patients will be observed for any signs of haematoma or bleeding. If there are no immediate complications, patients will be discharged on the same day.

These procedures will be performed either by vascular surgeons or interventional radiologists below tabled:

OPERATOR	FISTULOPLASTY		CENTRE	DESIGNATION
	ULTRASOUND-GUIDED	FLUOROSCOPY-GUIDED		
[name] [name]	✓		University Malaya Medical Centre	Vascular surgeon
TBD		✓	University Malaya Medical Centre	Interventional radiologist
[name] [name]	✓	✓	Hospital Kuala Lumpur	Vascular surgeon

Cases with serious complications such as extravascular leak or significant pseudoaneurysm will be admitted for monitoring. If the complications are resolved then, the patient will be discharged. Follow-up may be scheduled earlier.

Follow-up will be done at two weeks, one month, three months and six months.

Assessment during follow-up includes:

- Resolution of symptoms (prolonged post dialysis bleeding or difficult access cannulation).
- Reduction of venous dialysis pressure to below predefined threshold values. (the acceptable value is less than 150mmHg)
- Measurement of the volume flow (the acceptable value is more than 500ml/min), flow characteristics (the acceptable characteristic is laminar flow) and diameter of the target lesion (the acceptable diameter is between 5-6mm) using duplex ultrasound.

[figure not shown]
In the event of a negative outcome during the first post fistuloplasty follow-up, it will be determined whether it is due to:

- a missed stenotic segment invisible to ultrasound or
- it is a case of severe stenotic segment refractory to fistuloplasty.

Patients belonging to the former category will cross-over to the fluoroscopic-guided fistuloplasty group. In the latter case, there is no reason to repeat the fistuloplasty regardless of the imaging method (ultrasound or fluoroscopy). Ideally, these particular patients should receive drug-coated balloon (DCB) fistuloplasty which is beyond the scope of this study. There is no alternative apart from switching to fluoroscopic-guided fistuloplasty.

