3.3 Inclusion Criteria

NO.	INCLUSION CRITERIA	EVALUATION METHOD.
1	Patient able to comprehend English or Malay language.	Speak to patient.
2	Patient aged ≥ 18 years and ≤ 80 years.	Examine patient personal data.
3	Patient is willing to comply with protocol.	Ask the patient.
4	Native AVF that is able to provide prescribed dialysis consistently with 2 needles for $>2/3$ of dialysis sessions within 4 consecutive weeks.	Ask the patient & examine dialysis record.
5	Patient has a reasonable expectation of remaining on haemodialysis for 6 months.	Ask the patient.

6	Dampened thrill or pulsatile flow.	Palpate the arteriovenous fistula.
7	Volume flow (VF) <500 ml/min.	Ultrasound doppler measurement.
8	Severe stenosis (>50%) of arteriovenous (AV) access measured on color image and confirmed by peak systolic velocity (PSV) ratio of ≥ 3 in the inflow artery, anastomosis, or in the outflow vein.	Ultrasound doppler measurement.

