3.6 Sample Size

Based on a power of 80% ($\beta=0.2$), alpha of 0.05, a response anticipated difference of 90% in ultrasound-guided fistuloplasty group and 52.4% in fluoroscopy-guided fistuloplasty group, the calculated sample size for each group is 22 patients. Allowing for 20% dropout, a final sample size of 27 per group will be used.

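### Section 3.9 names tests that do not fit the outcome types: harmless for patency, but sparse secondary outcomes and volume flow are left without a suitable between-arm analysis

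*Combined protocol and SAP*

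**What the plan says.** Section 3.9 assigns two methods: "Independent t-test will be used to analyse the primary objective. Secondary objective will be analyzed using logistic regression". It adds descriptive summaries (mean and SD, or frequency and percentage), a 0.05 threshold and a per-protocol basis. It names no two-proportion, exact or survival method, and no other section does.

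The outcomes these methods must serve are:

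- **Patency.** Section 3.1: "The primary outcome would be to compare the patency of arteriovenous fistula at one, three and six months". The synopsis has "Patency of arteriovenous fistula over a period of six months post fistuloplasty". Section 3.6 sizes the trial on "a response anticipated difference of 90% in ultrasound-guided fistuloplasty group and 52.4% in fluoroscopy-guided fistuloplasty group", with no mean or SD.
- **Technical success and complications.** Section 3.1 lists both as secondary outcomes to be compared between arms.
- **Volume flow.** The synopsis lists "Percentage increase in volume flow" as endpoint (d). It does not appear among the synopsis's specific objectives or the secondary outcomes of section 3.1. Section 3.8 has flow measured at follow-up. Flow is also measured at screening, because section 3.3 requires "Volume flow (VF) <500 ml/min".

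**The concern.** A t-test compares means, patency is a yes/no status, and the sample size is a two-proportion calculation. The plan does not say what is being averaged.

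The secondary sentence refers to one objective, although section 3.1 lists several outcomes. It can be read two ways:

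- **Predictors of patency only.** Logistic regression then suits the task, but technical success, complications and flow have no named between-arm test.
- **All secondary outcomes.** Logistic regression is then applied to binary outcomes that may have no events in one arm. It also cannot be applied to flow, which is continuous.

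The method for the sparse outcomes could therefore be chosen after the data are seen, and different choices can fall on opposite sides of 0.05.

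**Working it through.** **Step 1. Reproduce the plan's figure.** Inputs from section 3.6: p1 = 0.90, p2 = 0.524, alpha 0.05 (two-sided assumed; not stated), power 80%, 1:1. The mean rate is 0.712.

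n = [1.960·√(2·0.712·0.288) + 0.842·√(0.9·0.1 + 0.524·0.476)]² / 0.376² = 21.55, so 22 per arm, as stated. This is the uncorrected two-proportion formula. A one-sided calculation with continuity correction also gives 22, and it too compares two proportions. With no mean or SD in the plan, a t-test sizing cannot be reconstructed. Section 3.6 says *response*; reading that as patency is an inference from the primary outcome.

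**Step 2. Does the t-test matter for 0/1 patency at one visit?** All pairs of binomial counts were enumerated at 0.90 vs 0.524:

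| Per arm | t-test | Uncorrected chi-square | Fisher |
|---|---|---|---|
| 22 | 82.6% | 82.6% | 73.6% |
| 27 | 89.4% | 90.6% | 82.8% |

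Maximum type I error over common rates of 0.50 to 0.95 at 27 per arm is 5.4% for the t-test, 5.7% for chi-square and 2.6% for Fisher.

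**Step 3. Chance that at least one arm has no events.** With event rates q1 and q2 and n per arm, this is 1 − [1 − (1−q1)^n]·[1 − (1−q2)^n]. The range runs from n = 27 (no dropout) to n = 22 (about 20% dropout). For complications at n = 27: (50/53)^27 = 0.207 and (86/90)^27 = 0.293, so 1 − 0.793·0.707 = 0.44.

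| Outcome and source | Rates | n = 27 | n = 22 |
|---|---|---|---|
| Complications, section 3.11 table, by counts | 3/53 vs 4/90 | 44% | 54% |
| Complications, by printed percentages | 3/53 vs 8/90 | 27% | 37% |
| Technical failure, Appendix 2 comparative study | 2/53 vs 6/90 | 45% | 55% |
| Technical failure, Appendix 2 series with 84% success, both arms | 7/43 | 2% | 4% |

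The second row is needed because the section 3.11 table prints 1/90 as 2.2%, whereas 1/90 = 1.1% and 2/90 = 2.2%. The complication rows assume one event per patient.

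**Step 4. What logistic regression reports with an empty arm.** Take 0/27 vs 3/27.

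- Odds ratio: no finite estimate. The Wald p is about 0.999.
- Likelihood ratio: 2·{[3 ln(3/27) + 24 ln(24/27)] − [3 ln(3/54) + 51 ln(51/54)]} = 2·(−9.419 + 11.586) = 4.34, p = 0.037.
- Fisher: 2·C(27,3)/C(54,3) = 2·2925/24804 = 0.236.

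By enumeration at 27 per arm, the nominal 5% likelihood-ratio test has type I error of 7.7% at a common event rate of 5%, rising to 8.8% at 6.7%.

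**Step 5. Could a better test rescue these comparisons?** No. At the comparative-study rates in Step 3, including the 8/90 reading, Fisher's power is 0.1–0.7% at 27 per arm and 0.3–1.3% at 22. At 27 per arm it needs a 6 vs 0 split (5 vs 0 gives p = 0.051).

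**Step 6. Volume flow.** Percentage increase is continuous, logistic regression needs a categorical outcome, and section 3.9 reserves the t-test for the primary objective. Only mean and SD remain. The percentage also depends heavily on baseline: 600 ml/min at follow-up is (600−499)/499 = +20% from 499, but (600−200)/200 = +200% from 200.

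**The case against.** The strongest reply is that little of this changes a result, and much of it stands.

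- **Primary.** A reader might infer that the t-test makes the primary analysis invalid or underpowered, or that it forfeits the effect estimate. Neither follows. Step 2 shows near-identical behaviour. The mean difference of 0/1 data is the difference in proportions, and it comes with an interval: at 24/27 vs 14/27 the t-test gives 0.370 (0.138 to 0.603), against 0.370 (0.148 to 0.593) from the usual Wald interval.
- **Months of patency.** A reader might suppose the t-test is meant for durations, where patients still patent at 6 months would be treated as exact times. The plan does not say so. Sections 3.1 and 3.6 point to status at fixed visits and a proportion, so no power loss can be charged to it.
- **Sparse outcomes.** Logistic regression is sound for binary outcomes in general, and its likelihood-ratio test still returns a p-value with an empty arm. It is workable at 84% technical success. These comparisons have almost no power under Fisher either. What remains is that the plan does not choose between Wald and likelihood ratio: the first is uninformative with an empty arm, and the second rejects too often at these rates.
- **Flow.** It is an endpoint but not a listed secondary objective, so purely descriptive reporting is a permissible reading. Whether a baseline-adjusted model has more power than a t-test on percentage increase depends on the scale on which the effect acts, which the documents do not give.

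**Conclusion.** The point holds as a mismatch between named tests and outcome types, to be corrected before the data are seen.

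For patency it is an alignment of test with sizing, with almost no numerical consequence on 0/1 status at one visit. It is not a rescue of validity or power.

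For technical success and complications it has substance if logistic regression is meant to cover them. At the comparative study's rates the chance of an empty arm is roughly even (27–37% for complications on the 8/90 reading), and the answer then turns on an unnamed choice. This depends on those rates carrying over: at 84% technical success the problem nearly disappears, and success definitions in the cited series may differ from section 3.1. If logistic regression covers only predictors of patency, the gap is instead that no test is named for these outcomes.

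For volume flow, no suitable between-arm test is assigned on either reading. No power figure is attached to that gap, because it would rest wholly on assumed inputs.

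**What to change.** Replace the two test sentences in section 3.9 with wording that does the following:

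1. **Patency.** Compare 6-month proportions by uncorrected chi-square, with the difference and 95% CI. Label the one- and three-month comparisons as supportive. This matches section 3.6 and leaves 22 per arm unchanged. Kaplan-Meier with log-rank is an optional supportive analysis; if used, it needs a stated date of loss and a censoring rule.
2. **Technical success and complications.** Use Fisher's exact test with an exact CI for the difference. State that these comparisons are essentially descriptive, since power is about 1% or less at the comparative-study rates.
3. **Volume flow.** Fit a linear model for flow at one named visit, adjusted for the screening flow already measured under section 3.3, and report percentage increase alongside.
4. **Logistic regression.** Keep it for predictors of patency, and say so.

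This needs no new patients or visits. The downsides are that Fisher is conservative, uncorrected chi-square reaches about 5.7% type I error at some common rates with 27 per arm, and there is slightly more analysis work. If SPSS 26.0 does not provide the exact interval, another package must be named.

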3.8 Study Visits and Procedures

Follow-up will be done at two weeks, one month, three months and six months.

Assessment during follow-up includes:

- Resolution of symptoms (prolonged post dialysis bleeding or difficult access cannulation).
- Reduction of venous dialysis pressure to below predefined threshold values. (the acceptable value is less than 150mmHg)
- Measurement of the volume flow (the acceptable value is more than 500ml/min), flow characteristics (the acceptable characteristic is laminar flow) and diameter of the target lesion (the acceptable diameter is between 5-6mm) using duplex ultrasound.

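### Optional: prespecify adjustment of the primary patency comparison for baseline volume flow, which every patient already has measured at entry

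*Combined protocol and SAP*

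**What the plan says.** Section 3.1 sets the primary outcome: "The primary outcome would be to compare the patency of arteriovenous fistula at one, three and six months". Section 3.6 sizes it as a proportion, with "a response anticipated difference of 90% in ultrasound-guided fistuloplasty group and 52.4% in fluoroscopy-guided fistuloplasty group". That yields 22 per arm, raised to 27 for dropout. Section 3.9 then says "Independent t-test will be used to analyse the primary objective". No covariate is named, and logistic regression is kept for the secondary objective, again without covariates.

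Baseline flow is available for everyone, because criterion 7 in section 3.3 requires "Volume flow (VF) <500 ml/min" on Doppler. Section 3.8 repeats the measurement at each visit: "Measurement of the volume flow (the acceptable value is more than 500ml/min". The synopsis lists percentage increase in volume flow as its own endpoint, (d), which also needs the entry value. Section 3.1 describes simple 1:1 randomisation and mentions no stratification. One secondary objective is to capture variables that may affect patency, but none is linked to the primary comparison.

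**The concern.** With simple randomisation and about 22 evaluable patients per arm, neither the design nor the planned analysis guards against the arms differing by chance in how poor the access was at entry. Baseline flow measures this and is already collected. If it predicts patency, leaving it out of the model gives up some precision. In a trial that happens to be imbalanced, the observed difference would also partly reflect the mix of patients. Adjustment chosen after the data are seen looks selective, so the decision has value only if it is made beforehand.

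**Working it through.** **1. The plan's own figure.** Inputs from section 3.6: p1 = 0.90, p2 = 0.524, alpha 0.05 (taken as two-sided), power 80%. The mean proportion is (0.90 + 0.524)/2 = 0.712.

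n = [1.960 × √(2 × 0.712 × 0.288) + 0.842 × √(0.90 × 0.10 + 0.524 × 0.476)]² / 0.376² = (1.255 + 0.490)² / 0.1414 ≈ 21.5, so 22 per group.

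Then 22 × 1.2 = 26.4, so 27 per group. Both stated figures reproduce. Power at 22 per group by this formula is 80.9%. No credit is taken for a covariate.

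**2. Linear approximation.** Adjustment multiplies the residual variance by (1 − ρ²), where ρ is the within-arm correlation of baseline flow with the 0/1 outcome. The documents give no ρ, so the values below are assumptions. The average within-arm SD is √[(0.09 + 0.2494)/2] = 0.412. By the noncentral t at 22 per arm, unadjusted power is 84.1%.

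| ρ (assumed) | Variance reduction | SE reduction | Adjusted power |
|---|---|---|---|
| 0.1 | 1% | 0.5% | 84.4% |
| 0.3 | 9% | 4.6% | 87.2% |
| 0.5 | 25% | 13.4% | 92.7% |

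**3. Simulation of the proposed model.** 20,000 runs, 22 per arm. Patency is a latent six-month value cut to give 90% and 52.4%, and r is the assumed correlation of baseline flow with that latent value. The adjusted analysis is a linear model with HC2-type robust errors.

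| r (assumed) | Unadjusted power | Adjusted power | Change in points (range over repeat simulations) |
|---|---|---|---|
| 0 | 82.7% | 82.0% | -0.7 to -0.9 |
| 0.3 | 82.3% | 83.0% | +0.7 to +1.3 |
| 0.5 | 82.2% | 86.7% | +4.2 to +4.7 |
| 0.6 | 83.1% | 89.2% | +6.0 to +6.3 |

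With patency 70% in both arms, the rejection rate was 4.7-5.0% unadjusted and 4.9-5.6% adjusted.

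The gains are smaller than in step 2 because r is not ρ. Dichotomising gives ρ = r × φ(z)/√[p(1 − p)], where φ is the normal density at the cut. At r = 0.5 this is 0.5 × 0.1755/0.300 = 0.29 in the 90% arm and 0.5 × 0.398/0.499 = 0.40 in the 52.4% arm. The simulation is the figure to rely on.

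**4. Entry restriction.** Criterion 7 cuts baseline flow at 500 ml/min. If the r values describe an unrestricted population, the correlation among enrolled patients is lower. For illustration, a normal baseline cut at its median (an assumption) turns 0.3 into 0.19, with no power gain, and 0.5 into 0.33, with a gain of about 1.5 to 2 points.

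**5. Chance imbalance.** The standardised difference in a baseline variable has SE √(2/n). P(|difference| ≥ 0.5 SD) = 2[1 − Φ(0.5/√(2/n))], which is 9.7% at 22 per arm and 6.6% at 27. With no true effect and 70% patency, such an imbalance moves the unadjusted difference by about r × 0.5 × φ(0.524) = r × 0.5 × 0.348. That is 5 points at r = 0.3 and 9 points at r = 0.5, against a planned difference of 90 − 52.4 = 37.6 points.

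**The case against.** Three stronger readings are tempting, and the documents support none of them.

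- **Flow is the baseline value of the primary outcome.** It is not. Patency is nowhere defined by a flow value, and occluded fistulas are excluded, so patency does not vary at entry. Flow is one of several follow-up measures, alongside symptoms, venous pressure, flow characteristics and diameter, and it has its own endpoint. The usual argument for adjusting for the same variable at baseline fits endpoint (d). For patency, flow is only a candidate predictor.
- **A patient entering at 150 ml/min has further to go to reach 500 than one entering at 450.** This leaves out the procedure. Section 3.1 ends the ultrasound-guided procedure at a flow above 500 ml/min, so a patient treated to that point has crossed the threshold whatever the entry value. Later failure depends on flow lost afterwards. Baseline flow may still matter, but this arithmetic does not show it.
- **Imbalance biases the planned test.** Under randomisation, chance imbalance is already covered by the test's error rate, as the null simulation shows. The 5- to 9-point shift is conditional on an imbalance seen in about one trial in ten.

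It is also fair to object that the correlation is assumed, that centre is a rival covariate because operators differ by centre and arm (section 3.1), and that section 3.9 has larger open matters: patency undefined, three time points, a t-test for an outcome sized as a proportion, and a per-protocol analysis. All of this stands and lowers the priority. It does not remove the point, since an unadjusted comparison of proportions would leave the same gap.

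**Conclusion.** The point holds as an optional efficiency measure and not as an error. The unadjusted comparison is valid as regards baseline balance, and the sample size in section 3.6 is unaffected. At 22 per arm, adjusting for baseline flow would change power by about -1 point (r = 0), +1 (r = 0.3), +4 to +5 (r = 0.5) or +6 (r = 0.6). The gain is worthwhile only towards the upper end of that range, and entry restriction could shrink it to between nothing and about 2 points for r of 0.3 to 0.5. Every figure for the gain rests on an assumed correlation and on patency behaving like a dichotomised latent variable; the documents confirm neither. The case for acting is the low cost, together with the need to settle the choice before results are seen.

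**What to change.** First define patency and fix six months as the primary time point. Then state in section 3.9 that:

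- the six-month patency difference is estimated from a linear model of patency (0/1) on arm and baseline volume flow (continuous, the value from criterion 7), with HC2-type robust standard errors and a 95% CI;
- the unadjusted difference is reported as a sensitivity analysis;
- if a time-to-event analysis is chosen instead, baseline flow enters the Cox model.

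A linear model keeps the result on the risk-difference scale. A logistic model would change the target to a conditional odds ratio. If the sponsor thinks centre is the more important covariate, that choice should be made and justified at the same point.

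The cost is a few lines of SAP text and no new measurements, provided the actual flow value is recorded and not only that the criterion was met. The downside is just under one point of power if baseline flow proves not to be prognostic.

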Arteriovenous fistulas (AVF) are the vascular access of choice for hemodialysis patients. In the United States from August 2010 to August 2013, arteriovenous fistula (AVF) use increased from 63% to 68% and across 20 other countries in 2013, arteriovenous fistula (AVF) use ranged from 49% to 92%.¹ Patency and functionality of haemodialysis access influences survival and quality of life for patients with chronic renal failure. Progressive narrowing of the perianastomotic lumen or a more proximal part of venous circulation as a result of intimal proliferation is the main cause of failure of arteriovenous fistula. The use of Doppler sonography allows identification of more than 50% arteriovenous fistula stenosis, with 92% sensitivity and 84% specificity.² Percutaneous transluminal fistuloplasty is a well-established therapeutic option for patients with haemodialysis vascular access stenosis. It is conventionally guided and monitored radiographically, but this carries the risks of ionizing radiation exposure and of adverse reaction to contrast media and this is the usual practice in Hospital Kuala Lumpur and University Malay Medical Centre.

Recently, we have observed an increasing role of ultrasonography (USG) in imaging of arteriovenous fistula. Superficial location of arteriovenous fistula allows for simple and reliable visualization of vessels, guidewire, catheter, balloon, etc., with significant technical advantages including the ability to directly visualize puncture sites, stenosis, thrombus, spasm, and extravascular flow in real time. Recent studies showed that percutaneous transluminal fistuloplasty can be performed under only sonographic guidance without using a fluoroscopic machine and it is as effective as conventional percutaneous transluminal fistuloplasty as shown in Appendix 1. Since more than a decade of described ultrasound-guided fistuloplasty, many small series have been published till date, but most of them studied small number population and without direct head-to-head comparison with fluoroscopy-guided fistuloplasty as shown in Appendix 2. To overcome these limitations and further evaluate the efficacy of the procedure, we would like to compare patency of arteriovenous access flow dysfunction post ultrasound-guided fistuloplasty versus fluoroscopy-guided fistuloplasty.

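### An undefined per-protocol set is the only analysis basis, while missed-lesion failures leave the ultrasound arm only; dropping or moving them can mask an ultrasound deficit of a few points

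*Combined protocol and SAP*

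**What the plan says.** Section 3.9 (Statistical Analysis Plan) closes with its only statement on the analysis population: "The data collected will be analyzed using an per protocol basis". No visible text defines that set or mentions an intention-to-treat analysis.

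Section 3.1 describes what follows a poor early result. The trigger is worded "In the event of a negative outcome during the first post fistuloplasty follow-up", and sections 3.1 and 3.8 place that visit at two weeks. One of two causes is then assigned. The first is "a missed stenotic segment invisible to ultrasound", for which the rule is: "Patients belonging to the former category will cross-over to the fluoroscopic-guided fistuloplasty group". The second is a stenosis refractory to the procedure. Here section 3.1 says first that "there is no reason to repeat the fistuloplasty regardless of the imaging method (ultrasound or fluoroscopy", and then: "There is no alternative apart from switching to fluoroscopic-guided fistuloplasty".

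The primary outcome in section 3.1 is patency at one, three and six months, so the crossover decision precedes every primary reading.

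**The concern.** A lesion that ultrasound guidance did not show is a failure of the method under test. By its definition this cause can arise only in the ultrasound arm, and no matching exit is described for fluoroscopy. The plan thus has a route out of one arm that opens after randomisation, depends on outcome, and comes before the first primary assessment.

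Under an undefined per-protocol basis, these patients could be dropped, counted under fluoroscopy, or kept under ultrasound with the rescued patency credited. Since the protocol itself directs the crossover, a per-protocol set could legitimately keep them. Without a written rule the choice could be made after results are known, and each of these options can flatter ultrasound. At stake is the size, and possibly the apparent direction, of the primary comparison.

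**Working it through.** **The plan's own figure.** Section 3.6 assumes 90% against 52.4%, 80% power and alpha 0.05. With the two-sided pooled formula without continuity correction and mean rate 0.712:

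n = [1.96 × √(2 × 0.712 × 0.288) + 0.842 × √(0.90 × 0.10 + 0.524 × 0.476)]² / 0.376² = 21.6, so 22 per group, as stated. Then 22 × 1.2 = 26.4, so 27 per group, as stated. The sample size makes no allowance for crossover.

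**Inputs for the bias.**
- f, the crossover share of the ultrasound arm: not given, so assumed.
  - Appendix 1: one-month primary patency in the ultrasound series is 100, 94.4, 93, 96, 100 and 100%, so all-cause loss is 0 to 7%. Missed lesions should be a subset, though these series may define patency differently.
  - 3.8% is the technical failure rate in the ultrasound group of the case-control study in Appendix 2 (2 of 53). It is a proxy only: fluoroscopy in the same study failed in 6 of 90 (6.7%), so it is not shown to be specific to ultrasound.
  - Working range: 3.8% to 7%.
  - Upper illustration: 8% to 10%. The 8% is the complement of the Doppler sensitivity in section 1 ("with 92% sensitivity and 84% specificity"). It is probably high, because inclusion criterion 8 already requires a lesion seen on ultrasound: "Severe stenosis (>50%) of arteriovenous (AV) access measured on color image".
- Q, patency of ultrasound patients without a missed lesion: 52.4% (the fluoroscopy rate in section 3.6), 77.6% (a six-month result from an ultrasound series in Appendix 1, illustrative only) and 90% (the ultrasound rate in section 3.6).
- P is fluoroscopy patency; r is the share of crossovers patent after rescue; h is the share of crossovers that would have been read as patent without crossover.

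**Dropped.** With crossovers counted as failures, true ultrasound patency is Q(1 − f). After dropping, the estimate is Q. Overstatement = Q × f, whatever fluoroscopy achieves.

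| f | Q = 52.4% | Q = 77.6% | Q = 90% |
|---|---|---|---|
| 3.8% | 2.0 | 2.9 | 3.4 |
| 7% | 3.7 | 5.4 | 6.3 |
| 8% (upper) | 4.2 | 6.2 | 7.2 |
| 10% (upper) | 5.2 | 7.8 | 9.0 |

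(percentage points)

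**If some crossovers would have been read as patent.** Overstatement = f(Q − h). At f = 7% and h = 50%: 0.07 × (0.776 − 0.50) = 1.9 points; 0.07 × (0.524 − 0.50) = 0.2 points.

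**Moved to fluoroscopy, with Q = P.** Overstatement = P × f + f(P − r)/(1 + f). At f = 7% and r = 0, 50 and 100%: 10.5, 7.2 and 4.0 points at P = 77.6%; 7.1, 3.8 and 0.6 points at P = 52.4%.

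**Kept, with rescue credited.** Overstatement = f × r. At f = 7%: 0, 3.5 and 7.0 points for r = 0, 50 and 100%.

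**Effect on the test.** Simulation of 400,000 trials per scenario: 27 per arm, 20% random dropout, Pearson chi-square without continuity correction, two-sided 0.05.
- Q = P and crossovers dropped: the expected difference is 0 and rejection stays at 5.1 to 5.3%.
- Q = P = 77.6%: the chance that the ultrasound estimate is at least as good as fluoroscopy rises from 42% as randomised to 51% dropped at f = 3.8%, and from 33% to 51% at f = 8%.

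**The case against.** The strongest reply is that the harm is small relative to the trial's precision. At f = 3.8% the overstatement is under one patient in 27 (1/27 = 3.7 points). With 22 evaluable per arm at 77.6% patency, the standard error of the difference is √(2 × 0.776 × 0.224/22) = 12.6 points. The 42% to 51% shift concerns the sign of the estimate, not a significance test. This stands, and it limits the severity. It does not remove the problem: the bias is systematic and runs towards the tested method if these patients, as failures, are dropped.

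It may also be said that the trigger is not wholly undefined, because section 3.1 lists acceptable values for pressure, flow, flow character and diameter just before it. That is fair. What is missing is how these values combine into a negative outcome. The flowchart is not shown and might state the analysed set; the point rests on the visible text.

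A reader might infer two stronger claims.
- *That the plan would produce a false finding of superiority.* This requires truly equal overall patency, so that ultrasound patients without a missed lesion do better than fluoroscopy patients: 77.6/0.92 = 84.3% against 77.6% at f = 8%. Section 3.11 instead expects essentially equal outcomes given adequate images, and in that case dropping creates no false superiority.
- *That a handful of crossovers would reverse the result.* With 21/27 against 24/27 (−11.1 points), dropping four ultrasound failures gives 21/23 against 24/27, or +2.4. But four of 27 is 14.8%, about twice the largest early loss in Appendix 1. Dropping two (7.4%) gives 21/25 against 24/27, or −4.9: the deficit is more than halved, not reversed.

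**Conclusion.** The concern holds as a should-fix. An undefined per-protocol basis, combined with a one-way early exit for ultrasound failures, leaves the primary comparison open to handling that favours ultrasound. If crossovers are dropped, the likely overstatement is about 2 to 6 points (f of 3.8% to 7%, Q of 52.4% to 90%), with 4 to 9 points as an upper illustration at 8% to 10%. It shrinks if some crossovers would have been read as patent anyway.

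Confidence in the direction is high if these patients are dropped or moved, and moderate for the size, because no crossover rate is given. The main harm is a masked ultrasound deficit in the estimate.

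Separately, the two section 3.1 sentences on refractory stenosis contradict each other, so the number of patients leaving the ultrasound arm by that branch cannot be determined.

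**What to change.** Replace the last sentence of section 3.9 with:

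> *The primary analysis includes every randomised patient in the arm assigned (intention to treat). A crossover or any other repeat intervention on the access counts as loss of primary patency in the assigned arm from that date. A negative two-week result, judged in both arms against the same acceptable values listed in section 3.1, is counted in the same way in both arms whether or not a repeat procedure follows. A defined per-protocol set is a sensitivity analysis, and crossover is not a reason for exclusion from it.*

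The third sentence matters. If only crossovers were scored as lost, the rule could count against ultrasound by f × h: at f = 7% and h = 25 to 50%, 1.8 to 3.5 points. The investigators should therefore write down, before outcomes are compared, how the listed values combine into a negative result. They should also define the per-protocol set and report crossovers by arm and by assigned cause. The sentences on refractory stenosis must be reconciled.

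The cost is analysis wording, with no new visits and no change to the stated sample size. The ultrasound estimate may be a few points less favourable. Power may also fall: if the planned 90% holds only for patients without a missed lesion, as-randomised power under the same simulation is about 72% at f = 3.8% and 59% at f = 8%, against about 80% with crossovers dropped. If 90% is the overall rate, there is no such loss.
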